This is an open label pilot study in which we will consent up to 25 subjects in order to treat 10 eligible subjects with probable mild to moderate AD. The study is single site and non-randomized. The subjects will be given rifaximin 550 mg orally twice daily for 3 months after evaluation to ensure they have no contraindications. Subjects at risk for drug interactions or tolerability issues may be started and/or maintained on a lower dose of 550 mg once a day. Individuals on concomitant drugs which are contraindicated per the package insert or in the investigators judgment will be excluded. Individuals on concomitant drugs which are not contraindicated but known to elevate blood levels SIGNIFICANTLY OR THOSE WITH MILD AEs (E.G. MILD DIARHEA) WILL receive qd dosing BASED ON CLINICIAN JUDGMENT. Consent, demographics, history, list of current medications, clinical and safety assessments, MMSE and blood tests (CBC, CMP, TSH, B-12 and Folic acid) will be performed at the Screening Visit. Medical history, physical exam, serum neuronal biomarkers and cytokines, serum ammonia level, Adverse Events and cognitive testing (ADAS-Cog-11) will be performed at the Baseline Visit. A stool sample collection kit will also be given to the subject and caregiver at the Baseline Visit, with instructions for use and how to get the sample back to the research coordinator. The stool sample will be obtained prior the subject taking the study drug. Medical history, physical exam, serum neuronal biomarkers and cytokines, serum ammonia level, Adverse Events and cognitive testing (ADAS-Cog-11) will be performed at the 3 month endpoint visit. A stool sample collection kit will also be given to the subject and caregiver at the baseline visit and 3 month Visit with instructions for use and how to get the sample back to the research coordinator. Interim safety checks will occur via phone calls one week after baseline and then every 2 weeks until the 3 month visit, which will then be followed by a 5 month phone call. Caregivers will be instructed to call the research coordinator or the PI ([name] after business hours or on weekends) if any change in stool is noticed at any time during the study. Unscheduled visit/labs may occur if warranted for safety based on clinical judgment. Because of a small risk of developing *C. difficile* up to 2 months following the last administration of rifaximin, the subjects will be followed for an additional 2 months after the 3 month treatment ends. Subjects who terminate early will receive the 3 month assessment at the time of termination.

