
Scientific Rationale for Study Design

This is an open label pilot study designed to provide preliminary evidence on the clinical efficacy of rifaximin in improving cognition in AD patients. We will be looking for improvement in test scores, changes in serum levels of neuronal markers and cytokines and changes in gut microbiota following treatment. We will also be collecting data

regarding the safety of long-term use of this non-absorbed antibiotic for this disease. This pilot may form the basis for a future larger randomized, double blind controlled study to further test this hypothesis. Statistical analyses will combined subjects on QD and BID for analyses as this is a pilot study and both doses may impact gut flora. In posthoc analyses we will put dosing as a covariate to examine dose effects.

Justification for Dose and Study Population

The rifaximin dosage and route of administration are the same as that used to treat hepatic encephalopathy, for which the drug and dosage are FDA approved. The dose will remain the same throughout the 3 month study of rifaximin administration unless stopped for safety reasons. The dose can be stopped or temporarily reduced for safety or tolerability reasons based on clinical judgment. The age and study sample of mild to moderate probable AD is similar to that used in AD prior trials. We will select our sample to be medically stable and free of hepatic disease and not having had recent antibiotic therapy to minimize risk for C Difficile infection.

End of Study Definition

The end of the study will occur 5 months after baseline testing and first administration of the drug. While drug administration will conclude and endpoint testing will be done at 3 months, we will continue to follow each subject for an additional 2 months, as C. difficile infectious diarrhea can occur up until 2 months after stopping an antibiotic.

Study Population

Inclusion Criteria

Subjects who meet the following criteria will be considered eligible to participate in the clinical study:

Probable Alzheimer's disease (National Institute of Neurological Disorders and Stroke (NINDS) criteria), mild to moderate severity

Ages 55-85; both genders

Mini Mental State Exam (MMSE) scores 10-22

Willing and able to comply with all scheduled clinic visits.

Stable medical health

Has a family or professional caregiver who has regular contact with subject

Ability to consent or legal guardian who can consent

Living at home or in a facility

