On no AD therapies or on stable (2 months) concurrent AD therapies

Exclusion Criteria

Subjects who meet one or more of the following criteria will not be considered eligible to participate in the clinical study:

Past history of C diff infection

Individuals on concomitant drugs which are contraindicated per the package insert or in the investigators judgment will be excluded

Assessment, laboratory examination, physical examination or any other medical condition or circumstance making the volunteer unsuitable for participation in the study in the judgment of the study clinicians

Allergy to Rifaximin

Antibiotic use in the last 6 months

Hospitalization in the last 6 months

Are taking medications that interact with Rifaximin

Are taking Cyclosporine

Past or current history of bloody stools or C Diff infection

Elevated LFTs

Clinically significant abnormal hepatic or renal function

Uncorrected thyroid or B12 abnormalities

Participation in another investigational drug trial in the past 30 days

History of febrile illness within 5 days prior to the study period

Hyperammonemia caused by:

Valproic acid

Chemotherapy

Lung transplant

Bariatric surgery

Ureterosigmoidoscopy

Hyperalimentation

Urinary tract infection

Errors of metabolism

Urea cycle

Enzyme deficiencies

Organic acidemias

Fatty acid oxidation

Amino acid transport defects

Lifestyle Considerations

Participation in the study will not have any impact on subject lifestyle.

Screen Failures

Volunteers who are consented to participate in the clinical trial and who do not meet one or more criteria required for participation in the trial during the screening procedures will not be rescreened later.

Strategies for Recruitment and Retention

Subjects will be recruited from referrals and the community via advertisement.

The study will be posted on clinicaltrials.gov.

Subjects and caregivers will be compensated for participation in the study at \$50 each per clinic visit to cover travel and time.

All tests and drug will be provided at no cost.

We expect to recruit 1 subject per month.

Study Intervention

Study Intervention Description

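### The two-month follow-up set for C. difficile risk has no scheduled contact between week 12 and week 20; one call at about week 16 would be a cheap backstop

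*Protocol*

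**What the plan says.** Study Design, Overall Design, sets safety calls at one week and then every two weeks until "the 3 month visit, which will then be followed by a 5 month phone call". The same section bases the extra two months on a small C. difficile risk lasting "up to 2 months following the last administration of rifaximin". End of Study Definition repeats the reason: "C. difficile infectious diarrhea can occur up until 2 months after stopping an antibiotic".

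The schedule table under Study Assessment and Procedures agrees with the text. Phone and AE assessments are marked at weeks 1, 3, 5, 7, 9 and 11, followed by the week 12 visit and then the week 20 call. Nothing is marked between weeks 12 and 20. As the table reads, the Bristol stool question is asked at baseline, week 12 and early termination, but not at week 20.

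Several safeguards apply throughout:
- Caregivers are told to call the coordinator or investigator "if any change in stool is noticed at any time during the study", with cover outside business hours. Unscheduled visits and labs are allowed (Overall Design).
- Entry requires that the subject "Has a family or professional caregiver who has regular contact with subject" (Inclusion Criteria).
- Exclusions include "Antibiotic use in the last 6 months", "Hospitalization in the last 6 months" and any past C. difficile infection (Exclusion Criteria).

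The Synopsis names adverse events as the primary safety endpoint. The Objectives and Endpoints table lists interim phone calls among the means of monitoring safety.

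**The concern.** The window exists for one named hazard, yet scheduled contact is thinnest there: the longest gap is 2 weeks on drug and 8 weeks after it. Some thinning is expected, because the on-drug calls also check compliance and can inform dosing. That does not explain having no call until the window closes.

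The caregiver route is real but narrow. The instruction concerns stool change. The Safety, Adverse Effects reporting and Management section also lists fever and abdominal pain among the signs of emerging C. difficile, and the instruction does not mention these. No caregiver trigger is stated for other adverse events. Subjects enter with "Mini Mental State Exam (MMSE) scores 10-22", so self-report cannot be relied on, and the caregiver criterion asks for regular contact, not daily contact or living together.

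At stake is earlier detection for an individual subject whose event is not volunteered, together with better recall of adverse events in follow-up. Known Risks describes C. difficile complications as ranging from mild diarrhea to fatal colitis, so a rare event can still matter.

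**Working it through.** **Inputs.** Contact weeks come from Overall Design and the schedule table: 0 (baseline), 1, 3, 5, 7, 9, 11 and 12 on treatment, then 20. The treated sample is 10 (Overall Design). The cited C. difficile incidences are 0.7% and 1.5% over 6 months on rifaximin in hepatic encephalopathy patients (Assessment of Potential Risks and Benefits).

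**1. Reproduce the schedule.** Gaps on treatment are 1, 2, 2, 2, 2, 2 and 1 weeks, so the longest is 2. After treatment there is one gap: 20 − 12 = 8 weeks. This matches the stated two months with one call.

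**2. Wait to the next scheduled contact for an event that is not volunteered.** Assume onset is uniform over weeks 12 to 20. The mean wait is Σ(gap²/2) ÷ 8.

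| Schedule | Gaps (weeks) | Longest wait | Mean wait |
|---|---|---|---|
| Current | 8 | 8 weeks | (8²/2)/8 = 4 weeks |
| With a week 16 call | 4, 4 | 4 weeks | (4²/2 + 4²/2)/8 = 2 weeks |

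The period a caregiver must recall at the week 20 call also falls from 8 to 4 weeks.

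**3. Absolute risk.** The documents give no post-treatment rate. For scale only, carry the cited on-drug rates into 2 of 6 months at constant hazard.
- Expected cases: 10 × 0.007 × 2/6 = 0.023; 10 × 0.015 × 2/6 = 0.050.
- Chance of at least one case: 1 − (1 − 0.007/3)^10 = 2.3%; 1 − (1 − 0.015/3)^10 = 4.9%.

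**4. Cases a call could affect.** This needs the share of events that caregivers do not volunteer, which the documents do not give. Assuming 10% to 30%, the range is 0.023 × 0.10 = 0.002 to 0.050 × 0.30 = 0.015 cases across the trial.

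**5. Cost.** 10 subjects × 1 call = 10 calls.

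**The case against.** The strongest reply is that this is a preference, because no stated aim goes unmet. The protocol names the risk, matches the follow-up to it and collects adverse events to month 5. The person told to report is the caregiver, not the impaired subject. By week 12 that caregiver has had six calls with AE assessment. The week 12 visit itself includes blood tests, an AE assessment and the stool question, and a stool kit is handed over then. The week 20 call can still record earlier events in retrospect. The possible gain, 0.002 to 0.015 cases, rests on an assumed non-reporting share and on on-drug rates moved to an off-drug period.

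Most of this stands, and it is why the point ranks as optional. The low absolute risk limits the importance of the change but does not close the gap. The caregiver trigger still covers only stool change, other adverse events still have no scheduled question for 8 weeks, and unscheduled visits help only once somebody has reported. The protocol's statement that its safety monitoring is adequate does not address the spacing of calls.

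A reader might infer that the post-treatment window is unmonitored. The documents do not support that, since caregiver reporting, after-hours cover and unscheduled visits run through month 5.

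**Conclusion.** The point holds as a cheap, optional improvement. In a window created for C. difficile risk, the single scheduled contact comes at its end. One mid-window call halves the longest scheduled wait (8 to 4 weeks) and the recall period for the primary safety endpoint. The fall in mean wait from 4 to 2 weeks depends on uniform onset, and every wait figure applies only to events that are not volunteered. How much recall would improve cannot be quantified from the documents.

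Three stronger readings go too far:
- A reader might treat the 24-hour watery-diarrhea criterion as a detection standard that this window fails. The protocol uses it as a rule for stopping the drug, and after week 12 there is normally no drug to stop.
- A reader might take 0.02 to 0.05 expected cases as a ceiling. Without a post-treatment rate that cannot be established. The protocol does say that affected patients in the cited trials had risk factors, and it largely excludes such subjects here, so far fewer than one case is a fair summary.
- A reader might think the trial's conclusions are affected. Efficacy and biomarker results do not depend on this call, and 10 subjects cannot support a C. difficile rate with or without it.

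**What to change.** Add one coordinator phone and AE assessment at about week 16, asking directly about diarrhea, any stool change, fever and abdominal pain. Keep the week 20 call, the caregiver instruction and the unscheduled-visit route unchanged.

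The change needs one new column in the schedule table and one sentence in Overall Design. It uses the existing coordinator and existing assessments, with no new procedure. The price is about 10 short calls and a little extra burden on caregivers and the coordinator. No efficacy endpoint, sample size or analysis changes.

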Recent evidence also points to a possibly more direct influence of gut bacteria on the brain. Terminal branches of the vagus nerve travel in close proximity to the intestinal barrier. Neurotransmitters and neuropeptides secreted by bacteria in the gut have been shown to activate vagal nerve ascending fibers, influencing brain function in mice. These effects ceased after vagotomy was performed. (Holzer et al 2014, Bravo et al, 2011)

Risk/Benefit Assessment

Known Risks

Risks of taking rifaximin, as listed on the package insert, are as follows.

Rifaximin is contraindicated in patients with hypersensitivity to rifaximin or rifamycin antimicrobials. Hypersensitivity reactions include exfoliative dermatitis, angioneurotic edema, and anaphylaxis. Clostridium difficile associated diarrhea is a risk whenever a patient is maintained chronically on antibiotics, with complications ranging from mild diarrhea to fatal colitis. Drug resistant bacteria can also result from long term use. There is increased systemic exposure to rifaximin in patients with severe hepatic impairment or in patients who are taking P-glycoprotein inhibitors concomitantly. Regarding use in geriatric patients, there were no reported overall differences in the safety of the drug when used in patients 65 years of age or over, when compared with younger subjects.

The most common reactions seen in patients taking rifaximin are:

Peripheral edema

Nausea

Dizziness

Fatigue

Ascites

Muscle spasms

Pruritis

Abdominal pain

Anemia

Depression

Nasopharyngitis

Arthralgia

Dyspnea

Pyrexia

Rash

Potential Benefits

Possible benefits that the subject may receive include the benefits of free medical testing and memory evaluations received at screening and during the study. Rifaximin is being used investigationally in this trial and hence it is not known if there will be any cognitive benefits. However, if there is ammonia toxicity in AD and the

drug were to be effective in lowering ammonia, then the subject may experience improvements in cognition.

Assessment of Potential Risks and Benefits

The available information suggests that the present clinical study has an acceptable risk-benefit ratio.

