Rifaximin (Xifaxan, Salix Pharmaceuticals, Bridgewater, N.J.) (See Package Insert) is a drug that is approved by the FDA for use in humans for the treatment of Hepatic Encephalopathy, Traveler's Diarrhea and Irritable Bowel Syndrome. It is commercially available. It will be used in accordance with approved labeling as pertains to dosage and administration for Hepatic Encephalopathy, contraindications and warnings. However, it will be used investigational in this trial as rifaximin is not FDA approved for the treatment of Alzheimer's Disease.

Safety, Adverse Effects reporting and Management

The AE monitoring schedule is described in the protocol. The drug will be discontinued immediately if there are emergent signs of C.Difficile (e.g. patient has watery diarrhea for longer than 24 hours, fever, abdominal pain or possible bloody stools). All AEs will be assessed by a study physician and referred for appropriate treatment. The study drug may be discontinued at any time per the study physician judgment for safety. All SAEs will be reported to the IRB within 24 hours of becoming aware of the event.

Dosing and Administration

The drug will be administered orally, under supervision of the caregiver, 550 mg twice a day, for 3 months.

Drug Acquisition and Accountability

The drug, rifaximin, will be provided by the study and acquired from the manufacturer. Compliance will be monitored at phone calls and accountability through pill counts at the endpoint study visit.

Formulation, Packaging, Appearance and Labeling

Rifaximin will be packaged in bottles of 100 tablets of 550 mg. The product will be dispensed under the supervision of the study clinician.

Product Storage and Stability

Rifaximin will be stored in the clinical study office in a double locked facility in conditions suitable for its stability.

Preparation

No special measures are required to prepare the drug for oral administration.

Measures to Minimize Bias: Randomization and Blinding

This is an open label pilot study. Objective tests and biomarkers are used to minimize bias.

Study Intervention Compliance

The subject's caregiver will be asked to keep a log of rifaximin dosage and date and time of administration. This will insure compliance and adherence to the study protocol. The compliance log and pill count will be reviewed during the endpoint visit.

Concomitant Therapy

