The subject may take concomitant medications that do not interact with rifaximin. These medications will be recorded at baseline. Any new medications taken during the study period will be recorded.

Rescue Medicine. AEs will be treated as appropriate with rescue medications.

Participant Discontinuation and Participant Discontinuation / Withdrawal

Discontinuation of Study Intervention

Administration of rifaximin will be discontinued and the study will be halted if a subject develops a severe hypersensitivity to rifaximin or if a subject develops a C. difficile infectious diarrhea with complications or any other AE felt by the clinician to warrant discontinuation.

Participant Discontinuation / Withdrawal from the Study

While subjects are encouraged to complete all study evaluations, they may withdraw from the study at any time and for any reason. Every effort will be made to determine why any subject withdraws from the study prematurely. This information will be recorded. All subjects who withdraw from the study with an ongoing AE will be followed until the event is resolved or deemed stable. If a subject withdraws prematurely, all data normally collected at the 3 month Visit will be collected at the time of premature discontinuation. Subjects who had to interrupt taking the study drug for any reason may be asked to go back on drug if there are no contraindications. Subject participation may be terminated prior to completing the study for any of the following reasons:

- Adverse event
- Protocol violation
- Loss to follow up
- Subject withdrew consent at own request
- Other

A Case Report Form (CRF) page will capture the date and the specific underlying reason for discontinuation of study intervention or participant discontinuation/withdrawal.

Study Assessment and Procedures

Efficacy Assessments

Rifaximin Alzheimer's Disease Study Pro00093318

	V1	V2							V3	V4/End	
Procedures	Screening	Baseline	wk 1	wk 3	wk 5	wk 7	wk 9	wk 11	WK 12 3 months	WK 20 5 months	Early Term
Consent	X										
Medical History	X	X							X		X
Concomitant Medications	X	X							X		X
Vitals	X	X							X		X
VeniPuncture	X								X		X
Blood Tests	X								X		X
Stool Sample		X							X		X
Physical Exam	X								X		X
MMSE	X								X		X
ADAS-COG-11		X							X		X
Study Medication Dispensation		X									
Study Medication Accountability									X		X
AE assesment	X	X	X	X	X	X	X	X	X	X	X
Phone Assessment			X	X	X	X	X	X		X	
Subject compensation		X							X	X	X
OnCore Status update	X									X	

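### The protocol's one caregiver call-in instruction names stool change, while its stop rules also rest on fever, abdominal pain and severe hypersensitivity

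*Protocol*

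**What the plan says.** The relevant text is all in the protocol; the SAP does not touch the point.

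- **Call-in instruction (Study Design, Overall Design).** Caregivers are to ring the coordinator, or the investigator out of hours, "if any change in stool is noticed at any time during the study". The protocol body names no other symptom as a reason to call.
- **Scheduled contacts (same section, and the schedule table under Study Assessment and Procedures).** Safety checks on treatment are "phone calls one week after baseline and then every 2 weeks until the 3 month visit". The table places the calls at weeks 1, 3, 5, 7, 9 and 11, with AE assessment at each, and the next clinic visit after baseline at week 12.
- **Immediate stop (Safety, Adverse Effects reporting and Management).** "The drug will be discontinued immediately if there are emergent signs of C.Difficile". The examples in brackets are: "patient has watery diarrhea for longer than 24 hours, fever, abdominal pain or possible bloody stools".
- **Separate stop (Discontinuation of Study Intervention).** Drug is discontinued and the study halted "if a subject develops a severe hypersensitivity to rifaximin". The same sentence adds complicated C. difficile diarrhea and any other AE that the clinician considers sufficient reason.

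**The concern.** A rule that says stop at once works only if the site learns of the event. Subjects enter with MMSE scores of 10 to 22, dosing is supervised by the caregiver, and no clinic visit is scheduled between baseline and week 12. Between phone calls, the caregiver is therefore the main route by which the site would hear of a problem. Clinician-judged discontinuation and unscheduled visits also depend on the site knowing first.

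The instruction given to that caregiver is narrower than the list of events on which the site is meant to act. A caregiver who follows the protocol's wording and goes no further would hold a fever, abdominal pain or a developing hypersensitivity reaction until the next call. These are not remote possibilities: Known Risks lists abdominal pain, pyrexia and rash among the most common reactions. Because severe hypersensitivity also halts the study, late notice could matter to other subjects. At the expected recruitment of 1 subject per month and 3 months of treatment, about 1 × 3 = 3 subjects could be on drug together.

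**Working it through.** **1. Stop signs against the call-in instruction.**

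| Stop sign in the protocol | Covered by a call for stool change? |
|---|---|
| Watery diarrhea beyond 24 hours | Yes, and earlier, since any change prompts the call |
| Possible bloody stools | Yes |
| Complicated C. difficile diarrhea | Yes, through the diarrhea |
| Fever (example sign of C. difficile) | Only if stool also changes |
| Abdominal pain (example sign of C. difficile) | Only if stool also changes |
| Severe hypersensitivity | No |
| Any other AE by clinician judgment | Cannot be listed in advance |

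**2. The plan's own interval.** A call at week 1 and then every 2 weeks gives weeks 1, 3, 5, 7, 9 and 11, with the visit at week 12. Text and table agree, and the stated interval is 2 × 7 = 14 days.

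**3. Gaps on treatment.** Contacts at weeks 0, 1, 3, 5, 7, 9, 11 and 12 give gaps of 7, 14, 14, 14, 14, 14 and 7 days.

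- Total: 7 + 5 × 14 + 7 = 84 days.
- Longest gap: 14 days.
- Days inside a 14-day gap: 5 × 14 = 70 of 84.

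**4. Doses in the longest gap.** Twice daily: 14 × 2 = 28 tablets. Once daily, which Overall Design allows for some subjects: 14 × 1 = 14 tablets.

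**5. Mean wait.** Assume that onset is uniform over the treatment period. The documents give no onset distribution. With gaps gᵢ, the mean wait to the next scheduled contact is Σ(gᵢ²/2) / Σgᵢ:

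(2 × 7² + 5 × 14²) / 2 / 84 = (98 + 980) / 2 / 84 = 539 / 84 ≈ 6.4 days.

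**6. Sensitivity.** If 3 months is read as 13 weeks, the last gap becomes 14 days. The maximum stays at 14, and the mean is (7² + 6 × 14²) / 2 / 91 = 612.5 / 91 ≈ 6.7 days. No call window is stated; one missed two-weekly call would make the longest gap 28 days. The 56 days from week 12 to week 20 are left out because no drug is taken then.

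**The case against.** There is a good case that little is wrong here, and much of it stands.

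- **The instruction is not exclusive.** A reader might infer that caregivers are told to call about stool and nothing else. The protocol does not say that. Nothing discourages other calls, and consent pages, a natural place for such instructions, are not in the text reviewed. What can be said is limited to the protocol body.
- **Fever and abdominal pain are examples.** A reader might take each as a stop rule in its own right. The rule is emergent signs of C. difficile, and these are illustrations of it. Elsewhere the protocol describes that infection as diarrhea, and for diarrhea the call-in threshold is more sensitive than the stop threshold. The residual gap is these signs without a stool change, plus severe hypersensitivity, which is a separate rule and does not depend on this reading.
- **There is no direct contradiction.** One passage says when caregivers call and the others say when drug stops; all can be obeyed together. That is true, but the protocol states a call-in rule, and that rule is narrower than what the site must act on.
- **Fourteen days of silent dosing is strained.** It needs an event that starts just after a call, is noticed, goes unreported, and is followed by continued doses from a caregiver who supervises dosing, keeps a dose log and has out-of-hours access. Anaphylaxis would probably prompt emergency care. Known rifaximin allergy is excluded. The scenario is more plausible for slower events such as a low fever or dermatitis.
- **Subjects may report for themselves.** The protocol does not say that they cannot, and it admits some who can consent. Reliance on the caregiver is an inference from the MMSE range and the supervised dosing.

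**Conclusion.** The mismatch is real and minor. The only call-in instruction in the protocol body names stool change; the stop rules also rest on fever and abdominal pain as example signs of C. difficile, and on severe hypersensitivity. For such a sign without a stool change, the protocol's next guaranteed question comes at most 14 days later during treatment, and about 6.4 days later on average under uniform onset. Both figures assume that calls are made on time and that the caregiver does not ring unprompted. The 28 tablets (14 if once daily) are a ceiling and should not be read as an expected exposure.

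It is also tempting to treat the reactions named in Known Risks as stop triggers: "Hypersensitivity reactions include exfoliative dermatitis, angioneurotic edema, and anaphylaxis". The documents do not support that. The sentence is part of a package-insert risk summary and is not limited to severe cases, whereas the discontinuation section speaks of severe hypersensitivity.

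With 10 subjects to be treated, few events are likely. The point is worth making because correction is nearly free and the protocol itself asserts, under Assessment of Potential Risks and Benefits, that its monitoring is adequate.

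**What to change.** Reconcile the call-in sentence in Overall Design with Safety, Adverse Effects reporting and Management and with Discontinuation of Study Intervention. The caregiver instruction should cover the stop signs the protocol already states, in the protocol's own wording: the example signs of C. difficile and severe hypersensitivity. The Known Risks list should not be imported as a set of triggers, and no stop rule, dose or call schedule needs to change. If the consent form or other caregiver material already says this, the protocol sentence should simply be brought into line with it.

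The cost is one sentence in the protocol, matching text in any caregiver material, and a few more calls to the coordinator.
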